6.1.3 Radiation Dose Specifications

SBRT will be delivered to a total prescription dose of up to 40-45 Gy in 5 fractions prescribed to PTV delivered every other day for an overall treatment time of two weeks. SBRT will be performed using either 6 MV photon beams on Varian TrueBeam STx system (Varian Medical Systems, Inc., Palo Alto, CA) with high definition (2.5 mm) leaflets or on the Accuray CyberKnife M6 (with or without HDI) (Accuray, Inc., Sunnyvale, CA).

The prescribed dose should cover at least 95% of the PTV. No more than 2% of PTV receives < 92% of the prescribed dose, except in the area adjacent to critical structures including spinal cord and brainstem, in which optimal sparing of these structures could not be achieved. In such instances, no more than 5% receives <80% of the prescribed dose may be permitted.

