6.2.2 Dosage and Administration

A cycle is defined as 28 days with M7824 administered on days 1 and 15.

Participants will receive an IV infusion of M7824 at a dose of 1200 mg over 1 hour (-10 minutes/+20 minutes, ie, over 50 to 80 minutes) on days 1 and 15.

Modifications of the infusion rate due to infusion-related reactions (IRRs) are described in Section 6.2.3. In order to mitigate potential IRRs, premedication with an antihistamine and with acetaminophen approximately 30 to 60 minutes prior to each dose of M7824 is mandatory for the first 2 infusions. Premedication is optional and at the discretion of the Investigator after the second infusion. If Grade \geq 2 infusion reactions are seen during the first 2 infusions, then premedication should not be stopped. Steroids as premedication are not permitted. Special precautions for monitoring of participants and management of IRRs/hypersensitivity, including modifications of the infusion rate and stopping of study drug are described in Section 6.2.3.

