13.2 Safety Lead-in

The Dose limiting toxicity (DLT) window for the combination of SBRT and M7824 in patients with recurrent HNSCC is from first M7824 administration (D1) until 14 days post SBRT (D28).

Patients will be administered 12 cycles of M7824 1200 mg intravenously every 2 weeks (Q2W), starting 2 weeks prior to the first fraction of SBRT until disease progression, intolerance, or consent withdrawal for up to 1 year. A cohort of 8 patients will be enrolled in the lead-in phase to assess safety and toxicity. More than 2 DLTs in 8 evaluable patients will be considered unacceptable.

With a cohort of 8 patients, the probability of the combination M7824 plus SBRT will be considered too toxic with a probability of 0.86 if the DLT rate is 50%. If the DLT rate is 0.20, the probability that the therapy will be deemed safe is 80%.

The phase 2 trial will proceed based upon the DLT data from the first 8 patients. Data from all patients will be evaluated when available.

This study will be monitored by the MD Anderson IND Office and a protocol-specific monitoring plan will be followed.

Bayesian toxicity monitoring will be applied to evaluate the safety profile of the treatment in the first 20 patients (including both Phase I and Phase II parts of the study). The first time of the toxicity monitoring will be in the cohort of the first 8 patients as described earlier. The treatment is considered too toxic if Probability (DLT rate > 0.3) > 0.6 . Based on the criteria and a prior distribution of the probability of toxicity as beta (0.3, 0.7), the patient enrollment will be halted if the numbers of observed DLTs exceed the following stopping rules:

at least 3 in 8, 4 in 9-11, 5 in 12-14, 6 in 15-17, and 7 in 18-20 patients.

If the stopping boundary is crossed, the results will be reported to the principal investigators and the study supporting company EMD Serono. The PI and supporting company EMD Serono will review this data to determine if the study design will need to be adjusted. By applying this rule, the following table shows the operating characteristics of the Bayesian toxicity monitoring rule. The results were obtained from the Bayesian toxicity monitoring program version 2.1.1 at <http://ibl.mdanderson.org/BTM/>.

Scenario	Prob.Of.Tox	Prob.Early.Stop	Prob.Declare.Tox	Avg.N.Patients
1	0.1	0.045	0.045	20.444
2	0.2	0.272	0.279	17.832
3	0.3	0.611	0.631	13.986
4	0.4	0.866	0.883	10.754
5	0.5	0.973	0.979	8.948

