13.5 Sample Size

The statistical considerations for the Phase I/II design are described as follows:

This is a phase I/II, open label, single arm study to evaluate M7824 plus SBRT in patients with locoregional recurrent HNSCC after prior head and neck radiotherapy that are not good candidates for salvage surgery (Figure 1). Patients must have evaluable disease by RECIST or RECIST 1:1 and a performance status ECOG 0-2. Time elapsed from prior radiotherapy must be at least 6 months.

Sample Size

In the phase I portion, 8 patients will be enrolled to access safety and toxicity. The primary endpoint is dose-limiting toxicity (DLT) defined as M7824 related \geq grade 3 adverse event (AE) unresolved to \leq grade 1 in \leq 28 days, or incomplete SBRT. DLT window is from first M7824 dose (D0) until 14 days post SBRT (D28). More than 2 DLTs in 8 evaluable patients will be considered unacceptable.

In the phase II portion, the primary endpoint is PFS at 1 year. Based on the prior studies [unpublished data from MD Anderson], we assume that the one-year PFS of the standard treatment is 0.60. If the new treatment improves the one-year PFS to 0.80 or higher, it will be considered a clinically important improvement. A sample size of 21 patients (with 1.5-year additional follow-up after the last patient is enrolled) will allow us to observe an improvement in 1-year PFS from 0.60 to 0.80. This will enable the study 80% power to detect the specified difference in PFS. Power was calculated using a log-rank test with a one-sided type 1 error rate of 0.10 (EAST 5.4 and STPLAN version 4.5). Based on our estimated accrual rate of 2 patients per month, we expect enrollment to be completed in 11 months. The total study duration is 29 months.

DMI (Data Management Initiative) database

Clinical data capture called DMI (Data Management Initiative) and CORe will be the electronic database used for this study's electronic case report forms.

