The student t-test or the Wilcoxon rank sum test will be used to compare continuous variables between patient groups. The chi-square test or the Fisher’s exact test will be applied to evaluate the association between two categorical variables. Logistic regression models will be used to evaluate the effects of the important patient clinical factors including treatment on PFS. The distribution of time-to-event endpoints will be estimated using the method of Kaplan and Meier. Comparison of time-to-event endpoints by important subgroups will be made using the log-rank test. Proportional hazards regression may be employed for multivariate analysis on time-to-event outcomes. PROs will be assessed at the completion of reirradiation, and subsequently every ± 3 -months until 24-months post reirradiation. Generalized linear models for the repeated measures analysis will be performed to assess the change in PROs overtime with important covariates including treatment in the models.

The Investigator is responsible for completing safety summary report, and submitting it to the IND Office Medical Affairs and Safety Group, for review and approval.

Lead in phase/phase I:

Toxicity summary will be submitted after the first eight evaluable patients’ complete 1 cycle of therapy.

Approval from IND office will be obtained before advancing to phase 2.

Phase II:

Toxicity summary will be submitted after first 3 evaluable patients’ complete 1 cycle of therapy and every 3 evaluable patients complete cycle 1 thereafter.

A copy of the cohort summary should be placed in the Investigator’s Regulatory Binder under “sponsor correspondence”.

13.7

Subject Identification and Privacy

A unique number will be assigned to each subject, immediately after informed consent has been obtained. This number will serve as the subject's identifier in the trial as well as in the clinical trial database. All subject data collected in the trial will be stored under the appropriate subject number. Only the Investigators will be able to link trial data to an individual subject via an identification list kept at the site. For each subject, original medical data will be accessible for the purposes of source data verification by the Monitor, audits and regulatory inspections, but patient confidentiality will be strictly maintained.

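### The lead-in toxicity summary is triggered at the end of cycle 1 (D28), before an open grade 3 or higher event from the combination phase can be scored as a DLT under Section 13.5

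*Combined protocol and SAP*

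**What the plan says.** **Trigger.** Section 13.6, lead-in phase: "Toxicity summary will be submitted after the first eight evaluable patients" complete one cycle of therapy. It adds: "Approval from IND office will be obtained before advancing to phase 2". Section 6.2.2 fixes the cycle length: "A cycle is defined as 28 days with M7824 administered on days 1 and 15".

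**Basis of the decision.** Section 13.2: "The phase 2 trial will proceed based upon the DLT data from the first 8 patients". More than 2 DLTs in 8 evaluable patients is unacceptable. The stated probability of calling the combination too toxic is 0.86 at a DLT rate of 0.50, and of calling it safe 0.80 at a rate of 0.20.

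**Exposure.** M7824 is given "starting 2 weeks prior to the first fraction of SBRT" (Section 13.2). SBRT is five fractions "delivered every other day for an overall treatment time of two weeks" (Section 6.1.3).

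**DLT window.** In Section 13.2 it "is from first M7824 administration (D1) until 14 days post SBRT (D28"). Section 13.5 repeats this end point but labels the first dose D0.

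**DLT definition.** There are two. Section 13.5 counts incomplete SBRT, or an M7824-related, at least "grade 3 adverse event (AE) unresolved to" grade 1 or less within 28 days. Section 12 counts a grade 3 or higher event, related to M7824 or the combination, that leaves the patient unable to complete radiotherapy. It has no resolution period.

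**The concern.** The lead-in exists to judge the safety of M7824 given together with SBRT. Its first two weeks are M7824 alone, so in cycle 1 the combination is seen only from about D15 to D28, and the trigger falls at the end of that span. One limb of the Section 13.5 DLT needs 28 days without resolution. A serious event that starts during SBRT and is still open when the eighth patient finishes cycle 1 has no DLT status under that limb yet.

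No text says to wait for such an event, or how to count it, before the request to advance. Following the stated trigger can therefore put the go decision before the phase I primary endpoint is determined in the last patients. The stated operating characteristics assume eight fully scored patients.

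**Working it through.** **1. Reproduce the plan's figures.** With 8 patients and 3 or more DLTs called too toxic:
- P(X ≥ 3 | n = 8, p = 0.50) = 1 − (1 + 8 + 28)/256 = 0.855 (stated 0.86).
- P(X ≤ 2 | n = 8, p = 0.20) = 0.797 (stated 0.80).

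The Beta(0.3, 0.7) rule of Section 13.2 also reproduces: the boundary is 3 in 8, 4 in 9–11, 5 in 12–14, 6 in 15–17 and 7 in 18–20, and the early-stop column is 0.045, 0.272, 0.611, 0.866 and 0.973. The figures are right, provided every patient counted has been fully scored.

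**2. Timeline in one patient.**
- First SBRT fraction: D1 + 14 = D15.
- Last fraction: D23 if strictly every other day (15, 17, 19, 21, 23), D24 on a Monday-Wednesday-Friday pattern, D28 if the full two weeks are used.
- At D28 the patient is therefore 0 to 5 days past the last fraction.
- Fourteen days after the last fraction is D37 to D42. D28 is about 14 days after SBRT starts, so the two halves of the window label do not agree.

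**3. When an unresolved event can be scored under Section 13.5.** Scoring day = onset day + 28.
- Onset D15: D43.
- Onset D28: D56.
- Onset D42, if the window runs that far: D70.

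**4. Patients affected at the trigger.** At the stated 2 patients per month, evenly spaced (assumption), entries are 365.25/24 = 15.2 days apart. When patient 8 is at D28, patient 7 is at about D43, patient 6 at D58 and patient 5 at D74.
- Window to D28, full scoring by D56: patients 8 and 7 are not fully scorable (2 of 8).
- Window to D42, full scoring by D70: patients 8, 7 and 6 are not fully scorable (3 of 8).

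**5. Effect on the chance of calling the combination too toxic.** Let k patients be pending and let f be the share of their DLTs that cannot yet be scored. Scored DLTs are the sum of Bin(8 − k, p) and Bin(k, p(1 − f)); the table gives the chance that this sum is 3 or more.

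| True DLT rate p | All 8 scored | k = 2, f = 0.5 | k = 2, f = 1 | k = 3, f = 0.5 | k = 3, f = 1 |
|---|---|---|---|---|---|
| 0.30 | 0.448 | 0.352 | 0.256 | 0.305 | 0.163 |
| 0.40 | 0.685 | 0.575 | 0.456 | 0.514 | 0.317 |
| 0.50 | 0.855 | 0.765 | 0.656 | 0.706 | 0.500 |

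The documents do not give f. The f = 1 columns bound the loss; f = 0.5 is an illustration.

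**6. Does later monitoring recover it?** Only in part. A third DLT in the first eight crosses the boundary at n = 8. If it is scored only after a ninth patient has been counted, the boundary is 4 and the same three DLTs no longer cross it.

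**The case against.** The case against has real force on scope and size.

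- **Not all combination toxicity is unscored.** A reader might infer that it is. The documents do not support that. Incomplete SBRT is known at about D28, and an event already resolved to grade 1 or less can be scored as a non-DLT. Only M7824-related grade 3 or higher events still open are pending.
- **The definition matters.** If Section 12 governs, there is no resolution wait, DLT status is known about when SBRT ends, and most of the calculated loss disappears. This stands. It is also a reason to reconcile the two definitions.
- **Nothing says open events count as zero.** A reader might infer this from the trigger. In fact cycle-1 completion prompts submission of a summary; advancing needs separate IND Office approval and is to rest on DLT data. The term evaluable is undefined and could mean evaluable for DLT. The plan is silent and does not direct a premature decision, but it does not prevent one either.
- **Other safeguards exist.** Bayesian monitoring runs through 20 patients, all data are to be evaluated when available, SAEs are reported promptly, and there is a separate monitoring plan not included in these documents. These help, but the step from 3 in 8 to 4 in 9–11 leaves the gap in working step 6.
- **Phase II summaries.** Those for every three patients use the same cycle-1 trigger, but they recur and are not described as gates, so a pending event can be updated in a later one. They are not a second instance of the same fault.

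**Conclusion.** The point holds in a limited form. The lead-in trigger can precede determination of the phase I primary endpoint, but only for M7824-related grade 3 or higher events from the combination phase that are still open at the trigger, and only if the Section 13.5 definition governs. The stated 0.86 is correct for eight fully scored patients and is not assured at the gate as timed.

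The values 0.66 and 0.50 should not be read as the design's true operating characteristics. They are a worst case that needs all of these together: Section 13.5 governs, accrual is even at 2 per month, no time passes between the eighth patient's D28 and approval, and every DLT in the last two or three patients is unscorable. On the finding's own timeline the last condition is strict, since patient 7 is at about D43 and an event with onset by D15 could already be scored. The actual loss lies between none and that bound, and the documents do not allow it to be placed more exactly.

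Separately, the window label contradicts itself under the stated SBRT schedule, so the window may itself run past the trigger.

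**What to change.** In Section 13.6, replace completion of cycle 1 as the lead-in trigger. Submit the summary, and the request to advance, when DLT ascertainment is complete in all eight patients: the window has closed and each patient's DLT status is determined under the governing definition.

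Reconcile the DLT definitions in Sections 12 and 13.5, the window label in Sections 13.2 and 13.5 (including D0 against D1), and the Section 13.6 trigger. Which clinical definition and window apply is for the sponsor and investigator; this review takes no position. Define evaluable at the same time.

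In the recurring phase II summaries, list events whose DLT status is pending and update them in the next summary.

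The cost is wording plus some time. If the window runs to about D42, the go decision moves by 42 − 28 = 14 days, even with no open event. With an open event the delay is at most 56 − 28 = 28 days (window to D28) or 70 − 28 = 42 days (window to D42), that is, about four to six weeks. Counting every open event as a DLT at the gate would avoid the wait, but it would set a new counting rule and lower the stated 0.80 chance of calling the combination safe by an amount that the documents do not allow one to compute. It is not proposed here.

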Grade 3 or Grade 4 – severe or life-threatening 
 Grade 3: Prolonged (e.g., not rapidly responsive to symptomatic medication and / or brief interruption of infusion); recurrence of symptoms following initial improvement; hospitalization indicated for clinical sequelae. Grade 4: Life-threatening consequences; urgent intervention indicated. 	
 Stop the infusion caused IRR immediately and disconnect infusion tubing from the participant with additional appropriate medical measures and close monitoring until deemed medically stable by attending Investigator. Hospitalization may be indicated. Restart the medication taking out the drug that is the cause of IRRs from the next scheduled visit

IV = intravenous, NCI-CTCAE = National Cancer Institute-Common Terminology Criteria for Adverse Event, and NSAIDs = nonsteroidal anti-inflammatory drugs.

Once the M7824 infusion is interrupted or rate reduced to 50% of previous infusion rate, it must remain decreased for all subsequent infusions. For Grade 3 or 4 IRRs, M7824 discontinuation is mandated.

For all types and grades of infusion reactions, details about drug physical constitution, method of preparation, and infusion must be recorded.

In the event of a Grade 2* IRR that does not improve or worsens after implementation of the dose modifications indicated in

Table (including reducing the infusion rate by 50%), the Investigator may consider treatment with corticosteroids and the infusion should be stopped for that day. At the next infusion, the Investigator may consider the addition of H2 blocker antihistamines (eg, famotidine or ranitidine), in addition to premedication, for select participants. However, prophylactic steroids are NOT permitted. At the next dose, if the participant has a second IRR Grade ≥ 2 on the slower infusion rate, with the addition of further medication to premedication, the infusion should be stopped and the participant removed from treatment.

Hypersensitivity Reaction

If a hypersensitivity reaction occurs, the participant must be treated according to the best available medical practice. A complete guideline for the emergency treatment of anaphylactic reactions according to the Working Group of the Resuscitation Council (United Kingdom) and can be found at <https://www.resus.org.uk/pages/reaction.pdf>. Participants should be instructed to report any delayed reactions to the Investigator immediately.

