If an ongoing SAE changes in its intensity or relationship to study drug or if new information becomes available, a follow-up SAE report should be sent within 24 hours to the EMD Serono (or designee) using the same procedure used for transmitting the initial SAE report.

All SAEs should be followed to resolution or stabilization.

The principal investigator will ensure that all SAEs in the clinical database are reported to EMD Serono and any applicable health authority during the conduct of the study.

SAEs will be reported on MDACC IRB approved form for prompt reporting (full form):

“Internal SAE Report Form for Prompt Reporting” Institutional Review Board.

SAEs will be submitted to both the Office of Protocol Research, Unit 1437 at The University of Texas MD Anderson Cancer Center and also sent to MEDWATCH

All SAEs should simultaneously be faxed or e-mailed to EMD Serono.

An SAE report should be completed for any event where doubt exists regarding its seriousness.

Definition of Dose Limiting Toxicity (DLT)

DLT for the combination of SBRT and M7824 in patients with recurrent HNSCC will be defined as:

1. Any \geq grade 3 AE resulting in inability to complete radiotherapy due to toxicity related to M7824 or the combination of M7824 and SBRT.

Drug destruction

Normal saline solution may be disposed of according to local site procedures. Other items used in the dose preparation and administration should be disposed of according to local site procedures.

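### The lead-in safety gate describes its eight patients in three ways, does not define evaluable for toxicity and has no replacement rule, so early leavers can bias it in either direction

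*Combined protocol and SAP*

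**What the plan says.** **Cohort.** Section 13.2 plans the lead-in as "A cohort of 8 patients will be enrolled in the lead-in phase to assess safety and toxicity". Its decision rule, which 13.5 repeats, is "More than 2 DLTs in 8 evaluable patients will be considered unacceptable". Later in 13.2 the basis for going on becomes "The phase 2 trial will proceed based upon the DLT data from the first 8 patients", without the word evaluable, followed by "Data from all patients will be evaluated when available".

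**Reporting and approval.** Section 13.6 reads "Toxicity summary will be submitted after the first eight evaluable patients" and ties submission to those patients finishing one cycle. It then states "Approval from IND office will be obtained before advancing to phase 2". The phase II summaries use the same cycle-1 trigger for every three evaluable patients.

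**DLT.** Section 12 counts an event of at least "grade 3 AE resulting in inability to complete radiotherapy due to toxicity related to M7824" or to the combination. Section 13.5 counts an M7824-related event of grade 3 or higher that has not resolved to grade 1 or less within 28 days, or incomplete SBRT, with no cause required for the latter.

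**Timing.** A cycle is 28 days (6.2.2). SBRT starts two weeks after the first M7824 dose (13.2) and takes two weeks overall, in five fractions given every other day (6.1.3). The DLT window runs to 14 days after SBRT, labelled D28 (13.2, 13.5).

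Elsewhere, evaluable describes disease on imaging (3.1, 7, 13.1). No section defines it for toxicity, and none provides for replacing a lead-in patient.

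**The concern.** The rule turns on a single patient: two DLTs in eight pass and three fail. How an early leaver is classified can therefore decide whether phase 2 opens.

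Two kinds of patient are left open. One stops during cycle 1 for toxicity and may or may not be among the eight who trigger the summary. The other leaves in the first two weeks, before any SBRT, because of progression or withdrawal. That patient could count as DLT-free, count as a DLT, or not count at all, depending on which sentence is followed.

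The quoted operating characteristics, and the Bayesian boundaries that continue to 20 patients, assume that every counted patient was fully assessed. A summary triggered by the end of a cycle may also be sent while the DLT window is still open.

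**Working it through.** **1. The plan's own figures.** Let X be the number of DLTs among 8 fully assessed patients, binomial with rate p. The treatment is too toxic if X ≥ 3.
- p = 0.50: P(X ≥ 3) = 1 − (1 + 8 + 28)/256 = 219/256 = 0.855. The plan states 0.86.
- p = 0.20: P(X ≤ 2) = 0.797. The plan states 0.80. The false alarm probability is 1 − 0.797 = 0.203.
- Boundary at 8: with the beta(0.3, 0.7) prior, P(rate > 0.3) is 0.638 after 3 DLTs and 0.340 after 2. Only the former exceeds 0.6, so 3 in 8 is right.

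The arithmetic is sound. The question is who the 8 are.

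**2. k of the 8 leave before SBRT for a non-toxicity reason.** The documents give no value for k; 0 to 2 is an assumed range. The other 8 − k patients have DLTs at rate p.
- Scored DLT-free (possible under section 12): P(Bin(8 − k, p) ≥ 3).
- Scored as DLTs (incomplete SBRT, 13.5): P(Bin(8 − k, p) ≥ 3 − k).

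For k = 1 and p = 0.50 these are 1 − (1 + 7 + 21)/128 = 0.773 and 1 − (1 + 7)/128 = 0.938. For k = 1 and p = 0.20 the second is 1 − 0.8^7 − 7 × 0.2 × 0.8^6 = 0.423.

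Probability of declaring the treatment too toxic:

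| k | p = 0.50, DLT-free | p = 0.50, as DLT | p = 0.20, DLT-free | p = 0.20, as DLT |
|---|---|---|---|---|
| 0 | 0.855 | 0.855 | 0.203 | 0.203 |
| 1 | 0.773 | 0.938 | 0.148 | 0.423 |
| 2 | 0.656 | 0.984 | 0.099 | 0.738 |

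**3. Patients with a DLT passed over because they did not finish cycle 1.** Section 13.6 permits this reading but does not state it. If a share f of DLT patients were passed over, the rate among those counted would be p(1 − f)/(1 − pf). At p = 0.50 this is 0.375/0.875 = 0.429 for f = 25% and 0.25/0.75 = 0.333 for f = 50%. The probability of three or more in 8 is then 0.741 or 0.532. Both values of f are assumptions.

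Steps 2 and 3 describe alternative denominators, so their effects do not add.

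**4. Timing.** With dose 1 on day 1, the first fraction falls on about day 15. Five fractions every other day end on day 15 + 8 = 23 at the earliest, or about day 28 on the stated two weeks. Adding 14 days gives about day 37 to 42. A 28-day cycle ends before that.

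**The case against.** The strongest reply is that 13.6 sets only the date on which a summary is sent, while the decision rule is in 13.2 and 13.5. A reader might infer that patients who stop in cycle 1 for toxicity are left out. No sentence says so. Both DLT definitions capture related severe toxicity that prevents completion of SBRT, and 13.2 adds "Data from all patients will be evaluated when available". This stands: exclusion is a possible reading, not an instruction. However, that sentence does not make the later data a condition of opening phase 2.

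A reader might also infer that the loose wording always makes the combination look safer. It does not. Under 13.5, a patient never given SBRT has incomplete SBRT and counts against the treatment.

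Nor does the rule on infusion reactions, "For Grade 3 or 4 IRRs, M7824 discontinuation is mandated", show that a DLT is lost. It stops M7824 and says nothing about SBRT, and 6.2.3 describes these reactions as generally resolving within 24 hours. A grade 3 reaction that resolves, in a patient who then completes SBRT, is a DLT under neither definition.

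The first eight may be shorthand for the first eight evaluable patients, and D28 would fit a window counted from the first fraction. Both are plausible, but the text does not settle either. IND office approval and Bayesian monitoring to 20 patients give further protection, though both rely on the same unsettled DLT count.

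**Conclusion.** The point holds as a defect of definition. The gate has three cohort descriptions, no toxicity meaning for evaluable, no replacement rule, and two DLT definitions that classify the same early leaver in opposite ways. The direction of bias cannot be stated until those definitions are reconciled.

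One such patient in eight moves detection at a DLT rate of 0.50 from 0.855 down to 0.773 or up to 0.938. On the 13.5 scoring, the false alarm probability at a rate of 0.20 goes from 0.203 to 0.423. These sizes assume one patient who leaves before SBRT for a non-toxicity reason, and independent DLTs at rate p in the others. The documents do not say how many such patients to expect.

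A reader might conclude that the stated 0.86 and 0.80 are wrong. They are correct for eight fully assessed patients; what is missing is a rule that secures eight such patients. The timing conflict is separate and depends on the window running from the end of SBRT.

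**What to change.** 1. Reconcile the DLT definitions in section 12 and 13.5, and the window dates (14 days after SBRT against D28). Which definition applies is for the sponsor and investigator to decide. The result should say how to class a patient who leaves before SBRT for a non-toxicity reason, and one who stops SBRT for toxicity that falls short of a DLT. Do this first, because a replacement rule added alone would silently override 13.5.
2. Put one DLT-evaluable rule in 13.2, 13.5 and 13.6. Every treated patient with a DLT counts, whenever treatment stopped. A patient without a DLT counts only if SBRT was given and the window was completed. A patient who is neither, under the reconciled definition, is replaced for the safety count but stays in the PFS analysis.
3. In 13.6, for both the lead-in and the every-three-patients phase II summaries, replace the cycle-1 trigger with having completed the DLT window or had a DLT. List all treated patients in each summary.

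With eight patients so defined, the stated 0.86 and 0.80 hold. The cost is wording in sections 12, 13.2, 13.5 and 13.6, a somewhat later gate, and possibly one or two more lead-in patients. At the planned two patients per month, those patients add about half a month to one month.
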